8 PARTICIPANT DISCONTINUATION/WITHDRAWAL

8.1 Discontinuation/Withdrawal

- A participant may withdraw from the study at any time at his/her own request or may be withdrawn at any time at the discretion of the investigator or sponsor for safety, behavioral, compliance, or administrative reasons. This is expected to be uncommon.
- At the time of discontinuing from the study, no further data will be collected for the participant.
- If the participant withdraws consent for disclosure of future information, the sponsor may retain and continue to use any data collected before such a withdrawal of consent.
- Participants who withdraw or discontinue the study early (e.g., prior to day-7 post procedure follow-up) may be replaced.

8.2 Lost to Follow-Up

A participant will be considered lost to follow-up if he or she repeatedly is unable to be contacted by the study site.

9 ADVERSE EVENTS AND DEVICE DEFICIENCIES

9.1 Definitions of Events

9.1.1 Adverse Events (AEs)

An AE is defined as any untoward medical occurrence, unintended disease or injury, or untoward clinical signs (including abnormal laboratory findings) in

participants, users or other persons, whether or not related to study device and whether anticipated or unanticipated (ISO 14155:2020). In this study, AE collection will be limited to those events judged by the investigator to be related or likely related to the neuraxial procedure and/or the BD Spinal Needles used in the procedure.

Pre-existing conditions should be considered as part of the participant's medical history and should not be reported as an AE unless there is a substantial increase in severity or frequency of the condition, which has not been attributed to natural history. Likewise, planned hospital visits and/or hospital stays should not be considered as adverse events. Exacerbation of an existing condition should be reported as an AE if the event meets the protocol definition of an AE.

The clinical course of the event will be followed according to accepted standards of medical practice until the event resolves, stabilizes, or in the opinion of the Investigator, is no longer considered clinically significant. The Investigator must supply the Sponsor with information concerning the follow up and/or resolution of the AE.

9.1.2 Serious Adverse Events (SAEs)

A serious adverse event is defined by ISO 14155:2020 as an adverse event that led to any of the following:

- a. death;
- b. serious deterioration in health of the participant, users, or other persons as defined by one or more of the following:
 - 1. a life-threatening illness or injury, or
 - 2. a permanent impairment of a body structure or a body function including chronic disease, or
 - 3. in-patient hospitalization or prolonged hospitalization, or
 - 4. medical or surgical intervention to prevent life-threatening illness or injury or permanent impairment to a body structure or a body function
- c. fetal distress, fetal death, a congenital abnormality or birth defect including physical or mental impairment.

9.1.3 Adverse Device Effect (ADE) / Serious Adverse Device Effect (SADE)

An adverse device effect is defined as any adverse event that is considered to be related to the use of an investigational medical device. This definition includes any event resulting from insufficiencies or inadequacies in the instructions for use, deployment, implantation, installation, or operation or any malfunction of the investigational device (study device) and includes any event that is a result of a user error.

A serious adverse device effect (SADE) is defined as an ADE that has resulted in any of the consequences characteristic of an SAE.

9.1.4 Unanticipated (Serious) Adverse Device Effect (UADE/USADE)

An unanticipated (serious) adverse device effect (UADE/USADE) is any (serious) adverse device effect on health or safety or any life-threatening problem or death caused by, or associated with, a study device, which by its nature, incidence, severity, or outcome has not been identified in the current instructions for use and/or current version of the risk analysis report, or any other unanticipated serious problem associated with a device that relates to the rights, safety or welfare of participants.

UADEs/USADEs will be reported to the appropriate governing body per ISO 14155:2020.

9.2 Severity of Adverse Events

Each AE shall be assessed for its severity, or the intensity of an event, experienced by the participant according to the criteria below.

Severity Rating	Description
Mild	Event, signs, or symptoms that do not interfere with the participant's daily activity, are usually considered self-limiting, can be treated with non-prescription type medications, and do not require medical intervention
Moderate	Event may interfere or cause low level inconvenience with the participant's daily activity. Requires medical intervention and/or treatment; however, unlikely to require hospitalization or be considered potentially life-threatening in nature
Severe	Event may cause significant discomfort to the participant and/or interferes with the participant's daily activity. Requires medical intervention and/or treatment to preclude a permanent impairment; may be life threatening and/or require hospitalization

9.3 Relationship of Adverse Event to Device(s)/Procedure

Each AE will be assessed for its relationship to the study device or procedure according to the following guidelines.

- A. Assess each AE for its relationship to the device or procedure.
 - Device Related: This category should be restricted to AEs directly attributable to the study device used in the neuraxial access procedure.
 - Procedure: A procedure includes any study-related activity performed during the neuraxial procedure.

B. The following categories shall be used for assigning the certainty of the relatedness.

Relatedness	Description
Not Related	Event is independent of study intervention and/or evidence exists that the event is related to another etiology. There must be an alternative etiology documented by the clinician.
Unlikely Related	Event in which the temporal relationship to study intervention makes a causal relationship improbable (e.g., the event did not occur within a reasonable time of the study device use) and in which underlying disease provides plausible explanations (e.g., the participant's clinical condition other concomitant treatments).
Likely Related	Event in which there is evidence to suggest a causal relationship and the influence of other factors is less likely. The event occurs within a reasonable time after use of the study device and is less likely to be attributed to concurrent disease.
Related	Event in which there is clear evidence to suggest a causal relationship and other possible contributing factors can be ruled out. The event occurs in a plausible time relationship to use of the study device and cannot be explained by concurrent disease.

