2.3.1 Risk Assessment

Potential Risk of Clinical Significance	Summary of Data/Rationale for Risk	Mitigation Strategy
Study Interventions: BD Spinal Needles		
In spinal procedures, larger diameter needles and cutting needle tips are both associated with an increased risk of post-dural puncture headache (PDPH)	Clinical literature (3; 4)	Physicians should select the smallest diameter needle sufficient to support the specific procedure
Study Procedures		
Neuraxial procedures may be associated with the following risks: 
 • Inadequate or failed anesthesia • Hemodynamic changes, most commonly hypotension • Post-dural puncture headache (spinal only) • Localized pain • Localized skin irritation • Urinary retention (temporary) • Nerve injury (rare) • Spinal-epidural hematoma (rare) • Infection 	Clinical literature (5; 6; 7; 8; 9)	
 • Physicians should select the smallest diameter needle sufficient to support the specific procedure • Patient blood pressure and heart rate should be closely monitored throughout the procedure and after medication administration • Only physicians with sufficient training and experience should perform neuraxial anesthesia procedures
Other		
Not applicable		

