**Table 14.3.1.1 Summary of Adverse Events**

## Evaluable Population

	(N=xxx)	
	By Events	By Subjects
Any Adverse Events	xxx	n (%)
Severity		
Mild	xxx	n (%)
Moderate	xxx	n (%)
Severe	xxx	n (%)
Relationship to Procedure 		
Related	xxx	n (%)
Likely Related	xxx	n (%)
Unlikely Related	xxx	n (%)
Not Related	xxx	n (%)
Relationship to Spinal Needle		
Related	xxx	n (%)
Likely Related	xxx	n (%)
Unlikely Related	xxx	n (%)
Not Related	xxx	n (%)
Relationship to Stylet		
Related	xxx	n (%)
Likely Related	xxx	n (%)
Unlikely Related	xxx	n (%)
Not Related	xxx	n (%)
Relationship to Introducer		
Related	xxx	n (%)
Likely Related	xxx	n (%)
Unlikely Related	xxx	n (%)
Not Related	xxx	n (%)
Relationship to Syringe		
Related	xxx	n (%)
Likely Related	xxx	n (%)
Unlikely Related	xxx	n (%)
Not Related	xxx	n (%)
Any Serious AE (SAE)	xxx	n (%)
Relationship to Procedure 		
Related	xxx	n (%)
Likely Related	xxx	n (%)
Unlikely Related	xxx	n (%)
Not Related	xxx	n (%)
Relationship to Spinal Needle		
Related	xxx	n (%)
Likely Related	xxx	n (%)
Unlikely Related	xxx	n (%)

(N=xxx)		
Not Related	xxx	n (%)
Relationship to Stylet		
Related	xxx	n (%)
Likely Related	xxx	n (%)
Unlikely Related	xxx	n (%)
Not Related	xxx	n (%)
Relationship to Introducer		
Related	xxx	n (%)
Likely Related	xxx	n (%)
Unlikely Related	xxx	n (%)
Not Related	xxx	n (%)
Relationship to Syringe		
Related	xxx	n (%)
Likely Related	xxx	n (%)
Unlikely Related	xxx	n (%)
Not Related	xxx	n (%)
Death	xxx	n (%)
Any ADEs 	xxx	n (%)

 The adverse event eCRF page requests the relationship with the surgical procedure and not with the procedure according to the protocol's definition, by mistake. A query was raised for every adverse event reported by the sites in order to clarify the issue and to update the adverse event page accordingly.

 ADEs are defined as any adverse events related or likely related to the spinal needle device.

For by-subject summaries, subjects are counted in the highest severity or most-related category.

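### Protocol 9.3 A defines device-related events more narrowly than the ADE definition in 9.1.3, so the SAP's ADE and SADE tables can miss use-related and use-error events

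*Protocol*

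**What the plan says.** Protocol 9.1.3 sets the definition: "An adverse device effect is defined as any adverse event that is considered to be related to the use of an investigational medical device". It then widens it: "This definition includes any event resulting from insufficiencies or inadequacies in the instructions for use, deployment, implantation, installation, or operation". Malfunction is also named, and the definition "includes any event that is a result of a user error". Seriousness is layered on top: "A serious adverse device effect (SADE) is defined as an ADE that has resulted in any of the consequences characteristic of an SAE".

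Protocol 9.3 gives sites their attribution guidance. Part A says of the device-related category: "This category should be restricted to AEs directly attributable to the study device used in the neuraxial access procedure". Beside it stands a broad alternative: "A procedure includes any study-related activity performed during the neuraxial procedure". Part B then grades the certainty of the relationship on four levels.

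The SAP turns the site's answer into the reported classification. Section 7 treats device-related adverse events and ADEs as the same thing, and footnote 2 to Table 14.3.1.1 gives the rule: "ADEs are defined as any adverse events related or likely related to the spinal needle device". The shells for Table 14.3.1.7 (ADEs) and Table 14.3.1.8 (SADEs) add no other rule. Neither document describes a separate ADE item on the case report form or a sponsor adjudication, and protocol 9.5 states that there is no safety committee.

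**The concern.** The definition and the coding instruction cannot both govern the same answer. Section 9.1.3 asks whether the event is related to use of the device, and a handling mistake counts. Section 9.3 A narrows the category to direct attribution to the device itself. A site that follows 9.3 A literally can code a use-error event to the procedure alone, and nothing downstream brings it back.

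At stake is whether the ADE and SADE tables report what the protocol says an ADE is. The study is meant to supply safety and performance data under EU regulation 2017/745, so a table carrying the ADE label should follow the protocol's own definition. Where sites read 9.3 A differently, the pooled count would also depend on which passage each site followed. The lean is towards under-counting, because 9.3 A is the narrower of the two.

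**Working it through.** No figure stated in the plan is at issue, so the check is a comparison of texts followed by an illustration of scale.

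**Step 1: trace event types through the rules.** The event types are my examples.

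| Event | ADE under 9.1.3? | Device related under 9.3 A, read literally? | In Tables 14.3.1.7/14.3.1.8? |
|---|---|---|---|
| Complication of a needle malfunction | Yes | Yes | Yes |
| Complication of a use error, needle sound | Yes | Not clearly; procedure category available | Only if the site still answers related or likely related to the needle |
| Complication of inadequate instructions, needle sound | Yes | Not clearly | Same condition |
| Skin reaction to antiseptic, no link to needle use | No | No | No |

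The two texts part company in rows 2 and 3. Because a SADE is a subset of the ADEs, a serious event in those rows drops out of both tables.

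**Step 2: look for a rule that repairs this.**
- SAP section 7 and footnote 2 rely on the needle answer alone.
- Protocol 9.6 makes use errors and inadequate manufacturer information device deficiencies. Table 14.1.13 tabulates them and Listing 16.2.4 lists them. No rule passes an associated adverse event on to the ADE tables, so one event could appear in Table 14.1.13 as associated with a use error and be missing from Table 14.3.1.7.
- Other outputs that use the needle answer, namely the ADE row of Table 14.3.1.1, the needle column of Table 14.3.1.4 and the ADE block of Table 14.3.1.9, inherit the same gap.

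**Step 3: check what is not affected.**
- Primary safety (SAP 5.1) uses the headache question on the follow-up page. Primary performance (SAP 5.2) uses the cerebrospinal fluid question. Neither uses relatedness.
- The secondary endpoint (SAP 5.3) counts an event if it is related or likely related to the procedure or to the needle. A procedure-only code still counts, and the event also appears in Table 14.3.1.5.
- Serious events appear in Table 14.3.1.6 whatever their attribution. Under protocol 9.4, SAEs and SADEs reach the sponsor by the same route within the same three working days.

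**Step 4: scale.** The number of misclassified events is not derivable, so counts of 0 to 3 participants are assumed. Rate = x/N, with 95% Clopper-Pearson limits. For x = 0 the upper limit is 1 − 0.025^(1/N); for N = 150 this is 2.43%. N = 150 is the planned maximum (protocol 4.1). N = 135 is 150 − 15, which applies only if enrolment stopped at 150 and none of the 15 untreated participants noted under SAP Table 14.1.1 was replaced.

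| Participants with an ADE | N = 150 | N = 135 |
|---|---|---|
| 0 | 0.00% (0 to 2.43) | 0.00% (0 to 2.70) |
| 1 | 0.67% (0.02 to 3.66) | 0.74% (0.02 to 4.06) |
| 2 | 1.33% (0.16 to 4.73) | 1.48% (0.18 to 5.25) |
| 3 | 2.00% (0.41 to 5.73) | 2.22% (0.46 to 6.36) |

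Each participant therefore moves the rate by 1/150 = 0.67 points, or 1/135 = 0.74 points.

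**The case against.** **Part B of 9.3 softens part A.** The likely-related grade asks only for evidence suggesting causation, its timing runs from use of the device, and the ADE rule accepts that grade. This is true. But part B grades certainty, while part A fixes what may be called device related. A site certain that a handling error caused the event still has to decide whether that is direct attribution to the device.

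**Needle and procedure are separate questions, so an event can be both.** This also stands, and it means procedure-only coding is a possibility, not something the documents state will happen. The form permits both answers but does not tell sites that a use error counts as needle-related.

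**Use errors are captured as deficiencies.** Protocol 9.6 adds that the ADE and SADE reporting provisions apply when a deficiency is associated with an adverse event. The events are therefore visible in the report, but they are not classified as ADEs in the tables that carry that name.

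**Post-dural puncture headache.** A reader might infer that every headache case is an ADE on one reading and none on the other, so that 150 × 0.003 = 0.45 to 150 × 0.03 = 4.5 expected cases move in or out. The documents do not support this. Section 9.3 does not mention the headache. Section 2.3.1 says of the needles that "larger diameter needles and cutting needle tips are both associated with an increased risk of post-dural puncture headache (PDPH", and also lists the headache among procedure risks. The all-or-none range would need every site to take the same extreme view. The headache is in any case counted in full as the primary safety endpoint.

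**Conclusion.** The mismatch is real and the SAP carries it into the outputs: an event can meet the ADE definition in 9.1.3 and be left out of Tables 14.3.1.7 and 14.3.1.8. That is as far as it goes. It affects a label and the descriptive tables built on it.

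Two stronger readings should be resisted. A reader might infer that the study's safety result is compromised. It is not: the safety endpoints are the headache and device- or procedure-related events, neither depends on this distinction, and SAP 2.8 sets no acceptance criteria. A reader might also infer that serious or unanticipated effects could go unreported or be under-tabulated. Reporting to the sponsor does not turn on the distinction, section 9.1.4 has its own wording covering effects caused by or associated with the device, and no table of unanticipated effects is planned.

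The size in this trial is unknown. It is 0.67 percentage points per affected participant if 150 are evaluable and 0.74 if 135 are, and it is zero if no such event occurred or if sites coded every such event to the needle as well. The conclusion assumes that sites used 9.3 as their guidance; eCRF completion instructions, which are not among the documents, could have said more.

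**What to change.** **Wording.** Align 9.3 A with 9.1.3, for example: *Device related: any adverse event related to the use of the study device, including one resulting from user error, inadequate instructions for use or malfunction. An event may be both device related and procedure related.* Put the same text in the eCRF completion guidance.

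**Data already collected.** Rewording does not change answers already given. Footnote 1 to Table 14.3.1.1 says a query was already raised on every adverse event because the form asked about the surgical procedure, so nothing can be added to that round. One of two steps is needed:
1. Send a short follow-up query asking sites to confirm the needle answer against the aligned wording, keeping the original answer in the audit trail.
2. Add a SAP derivation under which an adverse event associated with a use-error or labelling deficiency of the spinal needle counts as an ADE, and as a SADE if serious, in Tables 14.3.1.7 and 14.3.1.8.

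The query is the more complete remedy. The derivation reaches only errors that sites recorded as deficiencies, and it needs each deficiency to identify its adverse event; the shell of Listing 16.2.4 shows an association column but no event number.

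**Cost.** One paragraph in the protocol, plus either a small query round or a small programming step. The query asks sites to revisit causality after events are known, and the ADE count may rise.

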9.4 Reporting of Events

For all adverse events, all sections of the appropriate Case Report Form (CRF) must be completed.

All SAEs, SADEs, and/or UADEs/USADEs must be reported to the Sponsor via the electronic CRF without unjustified delay and within three (3) working days of the site/investigator becoming aware of the event.

It is the responsibility of the Investigator to report adverse events to individual Institutional Review Boards (IRBs)/Ethics Committees (ECs) and/or regulatory authorities according to the local regulations in each participating country.

9.5 Safety Committees

A safety committee will not be used in this study.

9.6 Device Deficiencies

Protocol Number: MDS-20EPSPEU001

CONFIDENTIAL

Version: 3.0

Date: 27Apr2022

The Investigator will record a device deficiency if a device used in the study, which is or appears to be inadequate with respect to its identity, quality, durability, reliability, usability, safety or performance due to mechanical failure, malfunction, or defect.

Device deficiencies also include use errors and inadequacy in the information supplied by the manufacturer including inadequate labeling. This applies to: devices used to treat the participant, or devices in which the package was opened, but the device was not used for treatment, or devices with which treatment was attempted, but the device did not remain through the entire study procedure/period.

All mechanical failures, malfunctions, missing components, and defects of the study devices will be recorded on the appropriate Case Report Form and will be promptly reported to the Sponsor. The device(s) should be returned to the Sponsor as outlined in the site's regulatory binder if requested.

If the device deficiency was associated with an AE, the reporting provisions for AEs, ADEs, SAEs, SADEs and UADEs/USADEs apply.

Reported deficiencies will be investigated and reported under 21 CFR part 803 Medical Device Reporting by the Sponsor if necessary, or as required by appropriate national laws and regulations. The site may be contacted to provide additional information to allow the Sponsor to conduct a thorough investigation.

It is the responsibility of the Investigator to notify the IRB/EC of such device deficiencies in accordance with the IRB/EC and/or the Competent Authority's local regulations.

9.7 Serious Health Threat

During the course of the study, device deficiencies or adverse events will be assessed if they constitute a serious health threat. The serious health threat is a signal from any adverse event or device deficiency that indicates an imminent risk of death or a serious deterioration in the health of subjects, users or other persons, and that requires prompt remedial action for other subjects, users or other persons. Serious health threat includes the possibility of multiple deaths occurring at short intervals, or other significant and unexpected serious adverse events that can be regarded as a potential serious health hazard in subjects, users or other persons and which are possibly related to the investigation device use.

10 STATISTICAL METHODS

The statistical analysis plan will be finalized prior to database lock and will include a more technical and detailed description of the statistical analyses described in the following sections. This section includes a summary of the planned statistical analyses of the primary and secondary endpoints.

Protocol Number: MDS-20EPSPEU001

CONFIDENTIAL

Version: 3.0

Date: 27Apr2022

10.1 Overview of Study Design

This is a multi-center, prospective, observational study to assess the overall safety and performance of the BD Spinal Needles.

10.2 Sample Size Considerations

The primary safety endpoint for spinal needles is the incidence of PDPH with an expected rate ranging from 0.3% to 3% based on literature review. With an incidence of PDPH of 3%, a sample size of 150 participants would lead to a precision of estimate less than 5% using Clopper Pearson exact method (precision of estimate is the distance between point estimate to the upper bound of 95% two-sided exact confidence interval). Additionally, with a sample size of 150 participants, the probability of observing at least one PDPH with is 91.1% when the expected rate of PDPH is 1.6%.

The primary efficacy endpoint for spinal needles is successful placement, defined as the spontaneous appearance of CSF, with an expected rate ranging from 90% to 100% based on literature review. With an expected placement success rate of 90%, a sample size of 150 participants would lead to a precision of estimate at approximately 5% using Clopper Pearson exact method.

